Secondary objectives (Arm B group)

- Time to and number of patients reinitiating treatment,
- Time to treatment failure after reinitiated treatment.

7 Study design

This study is designed as a phase 2 study with a late randomization in patients MRD negative after cycle 12 and 15, no formal comparisons between the two randomized treatment arms will be made.

During the treatment period all patients receive 15 cycles (28 days each) of oral ibrutinib + venetoclax treatment. During the first 2 cycles, only ibrutinib 420 mg a day is administered. From day 1 in cycle 3, ramp up over five weeks of venetoclax from 20 mg per day to the target of 400 mg per day is administered.

Patients achieving MRD negativity after cycle 12 in peripheral blood (PB) and at day 15 of cycle 15 in PB and bone marrow (BM) are randomized 1:2 between continuous ibrutinib treatment until toxicity or progression (arm A) and treatment free observation (arm B). Patients not reaching MRD negativity after cycle 12 and/or at day 15 of cycle 15 continue ibrutinib treatment until toxicity or progression (non-randomized patients).

MRD negative patients will be closely monitored for relapse/progression during the first 3 years after randomization by means of rapid reporting as described in section 16.1.1.

Patients becoming MRD positive (defined as $MRD \geq 10^{-3}$ and at least one month later $MRD \geq 10^{-2}$), or have symptomatic CLL according to IWCLL criteria (appendix A) during the observation period reinitiate treatment with both ibrutinib and venetoclax for 12 cycles and continue ibrutinib treatment until toxicity or progression.

Patients failing on reinitiating therapy (not reaching any response (CR/PR/SD) according to IWCLL criteria as assessed by the local investigator after 3 cycles of reinitiated therapy (or after reinitiation therapy until 12 months after randomization if progression occurred within 9 months from randomization) are considered as having progressive disease and will go off protocol treatment.

Details of all treatments (dose and schedule) are given in section 9.

8 Study population

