13.1 Primary endpoint

(Only considered for arm B of the study)

- ◆ Proportion of patients fulfilling the criteria for progression free survival (PFS) at 12 months after stopping therapy (27 months after starting treatment) for patients randomized to stop treatment. In this trial, reinitiated treatment due to MRD positivity will not be considered as progression, and symptomatic CLL according to IWCLL criteria within 12 months after randomization followed by reinitiation treatment resulting in a response (at least SD) before or at 12 months after randomization will neither be considered as progression.

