14.1 Patient numbers and power considerations

Treatment arms will be analyzed separately, only observation arm (arm B) will be considered for the primary end point. Only patients who are MRD negative after induction (i.e. MRD negative at both cycle 12 and at day 15 of cycle 15) will be randomized 1:2 for ibrutinib until progression (arm A) versus observation arm (arm B). It is expected that 45% of the registered patients will be randomized, based on the hitherto reported MRD negativity rates for venetoclax monotherapy and combination therapy with rituximab and the reported preclinical data on synergy between venetoclax and ibrutinib. The power calculation is based on the observation arm, at least equal or even better PFS is expected for the patients randomized for ibrutinib until progression. Patients who are MRD positive continuing on maintenance ibrutinib are expected to have a lower PFS than MRD negative patients.

The observation arm B is considered valuable if the PFS at 12 months after randomization is at least 75%. A success rate of less than 60% is considered not valuable for further investigation (in Phase III setting); this assumption is based on a 1-year PFS of 60% for RR CLL patients treated with FCR for the PFS endpoint (Fornecker, Am J Hem, 2015). No interim analysis on the primary endpoint is planned. An A'Hern one-stage design is used for the sample size calculation.

- Let P_0 be the largest success rate which, if true, implies that the therapeutic activity is too low and therefore does not warrant further investigation,. In the present trial, P_0 has been taken as 60%.
- Let P_1 be the smallest success rate which, if true, implies that the therapeutic activity is sufficiently high and therefore warrants further investigation in clinical trials. In the present trial, P_1 has been taken as 75%.

In order to reject the null hypothesis $H_0: P = P_0$ in favor of the alternative hypothesis $H_1: P = P_1$ with power $1 - \beta = 0.80$ (1-sided significance level $\alpha = 0.05$), 62 (eligible) patients are required in maintenance treatment arm with observation until progression (and at least 44 patients progression free at 12 months after randomization).

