14.4 Statistical analysis

14.4.1 Efficacy analysis

The PFS primary endpoint will be analyzed as soon as all randomized patients have achieved the landmark of 12 months after randomization. Thus, final analysis will take place as soon as the last patient starting treatment has reached the time point month 27 and data have been assembled from all study sites. Giving an estimated 3 years recruitment period, time point of final PFS analysis is projected 5 years and 6 months after trial initiation.

The primary efficacy endpoint is the investigator-assessed proportion of patients with PFS at month 27 in arm B, the ITT population for arm B is used for calculation of the proportion. PFS is defined as all patients free of progression or relapse (determined using standard IWCLL guidelines [2008], appendix A), or death from any cause, whichever occurs first. Patients in the observation arm becoming MRD positive thus restarting treatment are still considered progression free, as long as they don't progress according to IWCLL criteria after start reinitiation treatment. If patients in the observation arm have clinical progression but achieve response within three months of reinitiating treatment, they are still considered progression free. For patients reinitiating therapy before 27 months according to the rules outlined above who have progressed according to IWCLL criteria before reinitiating treatment are allowed up to 3 months after reinitiating therapy to obtain response. These patients will be considered progression free at month 27 if a response is achieved within 3 months from reinitiating therapy.

The primary objective of the study is to test the following hypothesis:

The progression free survival rate at 12 months after randomization for the observation arm (B) is more than 60% (i.e., H_0 : PFS rate at 12 months post-randomization \leq 60% versus H_1 : PFS rate at 12 months post-randomization $>$ 60%). PFS and the 95% confidence interval (CI) will be estimated using Kaplan-Meier survival methodology, and a Kaplan-Meier survival curve will be generated to

provide a visual illustration of PFS for patients in the different treatment arms separately (from randomization), and also for all patients together (from registration).

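### Sections 13.1 and 14.4.1 classify a rescued clinical progression differently in the primary endpoint, and the month-27 analysis trigger does not fit the 14.4.1 window

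*Protocol*

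**What the plan says.** Two sections of the protocol define the primary endpoint, the proportion of arm B progression free 12 months after stopping therapy. The protocol equates that time with month 27 from treatment start.

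- **Section 13.1 (Primary endpoint).** Symptomatic CLL within 12 months of randomization is not counted as progression if treatment is restarted, "resulting in a response (at least SD) before or at 12 months after randomization". No limit is set on time since restart.
- **Section 14.4.1 (Efficacy analysis).** For patients who progress and restart before month 27: "These patients will be considered progression free at month 27 if a response is achieved within 3 months from reinitiating therapy". There is no 12-month limit, and the section does not say whether stable disease (SD) counts as a response.

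Two other sections label non-responders to restarted therapy as having progressive disease and take them off protocol treatment.

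- **Section 7 (Study design).** The limit is 3 cycles, or restarted therapy "until 12 months after randomization if progression occurred within 9 months from randomization".
- **Section 9.4.** The limit is 3 cycles, without the 9-month clause.

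On timing, section 14.4.1 states that the "final analysis will take place as soon as the last patient starting treatment has reached the time point month 27" and the data have been assembled. Analysis VI in section 14.4.4 has the same trigger. Section 14.4.1 projects the analysis at 5 years 6 months after trial initiation.

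**The concern.** This is the only confirmatory test in the trial. It compares a count of successes with a fixed bar of 44 out of 62. If the definition of a success depends on which section is applied, so may the result. The trial is open-label, the endpoint is investigator-assessed, and interim reports to the DSMB show progressions and restarts in arm B, so the rule should be unambiguous before those data are seen. In addition, if the 14.4.1 window applies, some patients may not yet have a status when the stated trigger is reached.

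**Working it through.** **1. The plan's own figure.** Inputs from section 14.1: "P_0 has been taken as 60" percent, "P_1 has been taken as 75" percent, 0.05 as the "1-sided significance level", power 0.80, n = 62, success if at least 44 are progression free. Exact binomial:

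- P(X ≥ 44 | n = 62, p = 0.60) = 0.0492
- P(X ≥ 44 | n = 62, p = 0.75) = 0.812

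The smallest n with error at most 0.05 and power at least 0.80 is 62, with bar 44. The design reproduces.

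**2. The two endpoint rules side by side.** Let *t* be the month of restart after randomization (taken as the month of progression) and *r* the month of first response.

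- 13.1: success if r ≤ 12.
- 14.4.1: success if t is before month 12 and r ≤ t + 3.

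The rules agree only where both limits are met or both are missed.

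- For t > 9, a response with 12 < r ≤ t + 3 fails 13.1 and passes 14.4.1.
- For t < 9, a response with t + 3 < r ≤ 12 passes 13.1 and fails 14.4.1.

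Neither rule is always the more lenient. Examples:

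| Progression and restart | First response | 13.1 | 14.4.1 |
|---|---|---|---|
| Month 11 | Month 13.5 | failure (13.5 > 12) | success (13.5 ≤ 14) |
| Month 4 | Month 9 | success (9 ≤ 12) | failure (9 > 7) |

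**3. The off-treatment text.** Cycles last 28 days (section 9.1), so 3 cycles = 84 days = 84/30.44 = 2.76 months, against about 91 days for 3 months. Section 7 follows the 13.1 limit for progression within 9 months. For later progression it comes close to 14.4.1, but in cycles. Section 9.4 uses 84 days throughout. For progression at month 10 with first response at month 12.9 (day 88), sections 7 and 9.4 give progressive disease, 13.1 a failure and 14.4.1 a success.

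**4. Timing.** A restart just before month 27 gives a 14.4.1 window closing just before 27 + 3 = month 30. In calendar time, with 3 years of recruitment:

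- trigger: 36 + 27 = 63 months
- last window closes: 36 + 30 = 66 months
- projected analysis: 5 years 6 months = 66 months
- last window if the last patient starts 28 days after registration, as section 9.1 permits: 66 + 0.9 = 66.9 months

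**5. How many patients.** The protocol gives no clinical progression rate for arm B. Assume 5% to 25%, spread evenly over 12 months. Progressions in months 9 to 12:

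- 62 × 0.05 × 3/12 = 0.8
- 62 × 0.25 × 3/12 = 3.9

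Only those who first respond after month 12, but within 3 months of restart, are discordant.

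**6. What each patient does to the test.** If the true rate is 60% under the stricter reading and the other reading adds *k* successes, the effective bar is 44 − k:

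| Patients added | Effective bar | P(X ≥ bar), p = 0.60 |
|---|---|---|
| 0 | 44 | 4.9% |
| 1 | 43 | 8.3% |
| 2 | 42 | 13.2% |
| 4 | 40 | 27.8% |

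In the other direction, losing one success at a true rate of 75% (effective bar 45) lowers power from 81.2% to 72.6%.

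**The case against.** The strongest reply is that the conflict is narrow. The synopsis refers to 13.1 for details, which suggests that 13.1 governs. Response is assessed at the end of cycle 3 after restart (Table 10.2.3) and with CT at month 27, so most rescued patients would be classified alike under both sections. Section 14.4.6 provides for an SAP before the final analysis and says that deviations may not affect the primary analysis.

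Much of this limits the point, and several stronger readings that a reader might infer do not stand:

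- **Three competing endpoint rules.** Sections 7 and 9.4 mainly decide who leaves protocol treatment. They matter because they label patients as having progressive disease, but the endpoint itself is defined in 13.1 and 14.4.1.
- **A different response threshold.** Sections 7 and 9.4 list SD among responses and 13.1 says at least SD. No section sets a higher threshold, so the silence of 14.4.1 is a gap in wording.
- **Slow response after early progression.** This needs progressive disease to persist beyond 3 months of restarted therapy and then resolve. With the cycle 3 evaluation and the off-treatment rule in 9.4, it should be rare.
- **An analysis date before the window closes.** The projected date of 66 months just reaches the end of the window. The conflict is with the month-27 trigger.
- **A licence to choose the rule after seeing data.** The text is ambiguous, but it grants no such choice.

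What the reply does not remove is the late progressor. For that patient the two defining sections give opposite results, and the reference in the synopsis does not withdraw the explicit 3-month allowance in 14.4.1. An SAP may say more, but because 14.4.6 bars it from altering the primary analysis, it cannot be assumed to settle which section prevails.

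**Conclusion.** The point holds for the core conflict. Sections 13.1 and 14.4.1 use different reference times, so a patient progressing in months 9 to 12 and first responding after month 12 is a failure under one and a success under the other. The month-27 trigger does not allow for the 14.4.1 window, and the projected date covers it with no margin.

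The number affected is probably small: at most the 0.8 to 3.9 patients who progress in months 9 to 12, on an assumed even 5% to 25% progression rate, and fewer once those responding by month 12 are set aside. The test is still sensitive, since one reclassified patient takes the error from 4.9% to 8.3% and two take it to 13.2%. The 27.8% figure requires four patients all to flip the same way. It is an upper case and should not be read as the expected error. The sample size of 62 and the bar of 44 are unaffected.

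**What to change.** Before any arm B outcome data are reviewed, the sponsor should:

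1. Reconcile 13.1 and 14.4.1 into one endpoint classification rule that fixes the reference date, the unit (months or cycles) and whether SD counts.
2. State that rule identically in the synopsis, 13.1 and 14.4.1.
3. Set the trigger in 14.4.1 and Analysis VI so that every patient's window has closed.
4. Report the other version as a named sensitivity analysis.

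Reading status at 12 months after randomization, as in 13.1, is one option, and for the primary analysis it needs no later data cut. If the 3-month window is kept, the cut-off moves to month 30 for the last patient. Under the first option, the sensitivity analysis would need that later cut.

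The off-treatment rules in sections 7 and 9.4 differ from each other and from the endpoint text. The sponsor must reconcile them; no clinical rule is proposed here.

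The cost is a wording amendment and, depending on the rule chosen, up to 3 months' delay in the data cut. The sample size does not change.

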13.2 Secondary endpoints

Secondary endpoints (for all treatment groups: MRD positive non-randomized patients, patients MRD negative after cycle 12 and at day 15 of cycle 15 randomized for ibrutinib maintenance (arm A) or observation (arm B)):

- ◆ Minimal residual disease (MRD) at 12 months after stopping treatment (month 27) for patients randomized to stop of treatment.
- ◆ PFS of all study groups.
- ◆ Time to and number of patients reinitiating treatment
- ◆ Time to treatment failure after reinitiated treatment
- ◆ Time to next CLL treatment
- ◆ MRD after cycle 12 (PB), at day 15 of cycle 15 (PB and BM) and at later time points in PB
- ◆ Overall survival (OS)
- ◆ Complete response (CR)/ Partial Response (PR)/ Stable disease (SD) after cycle 3, 9, 12, 15 and month 27 and month 51 (3 years after stopping treatment)
- ◆ Duration of response
- ◆ Safety parameters: Type, frequency, and severity of
 - adverse events (AEs) and
 - adverse events of special interest (AESI) and their relationship to study treatment
- ◆ Health-related quality of life (QoL) by EORTC QLQ-C30 and QLQ-CLL16 questionnaires
- ◆ Exploratory endpoints:
 - ◆ Evaluation of relationship between various baseline markers and clinical outcome parameters
 - ◆ Various markers at time of progression
 - ◆ Correlation between MRD in BM and PB
 - ◆ Correlation between MRD in BM and PFS/OS
 - ◆ Correlation between MRD in PB and PFS/OS

14 Statistical considerations

This study is designed as a phase II study with upfront registration and a late randomization for patients who are MRD-negative at 12 and 15 cycles. The primary objective of the study is to evaluate in arm B the efficacy of ibrutinib + venetoclax (VI) in terms of PFS 12 months after stopping treatment for patients achieving MRD negativity after cycle 12 and at day 15 of cycle 15 in previously treated patients with CLL (arm B). The patients in arm A and the non-randomized patients are only considered for secondary and exploratory endpoints, and no formal comparison between randomized patients are made.

14.1 Patient numbers and power considerations

Treatment arms will be analyzed separately, only observation arm (arm B) will be considered for the primary end point. Only patients who are MRD negative after induction (i.e. MRD negative at both cycle 12 and at day 15 of cycle 15) will be randomized 1:2 for ibrutinib until progression (arm A) versus observation arm (arm B). It is expected that 45% of the registered patients will be randomized, based on the hitherto reported MRD negativity rates for venetoclax monotherapy and combination therapy with rituximab and the reported preclinical data on synergy between venetoclax and ibrutinib. The power calculation is based on the observation arm, at least equal or even better PFS is expected for the patients randomized for ibrutinib until progression. Patients who are MRD positive continuing on maintenance ibrutinib are expected to have a lower PFS than MRD negative patients.

The observation arm B is considered valuable if the PFS at 12 months after randomization is at least 75%. A success rate of less than 60% is considered not valuable for further investigation (in Phase III setting); this assumption is based on a 1-year PFS of 60% for RR CLL patients treated with FCR for the PFS endpoint (Fornecker, Am J Hem, 2015). No interim analysis on the primary endpoint is planned. An A'Hern one-stage design is used for the sample size calculation.

- Let P_0 be the largest success rate which, if true, implies that the therapeutic activity is too low and therefore does not warrant further investigation,. In the present trial, P_0 has been taken as 60%.
- Let P_1 be the smallest success rate which, if true, implies that the therapeutic activity is sufficiently high and therefore warrants further investigation in clinical trials. In the present trial, P_1 has been taken as 75%.

In order to reject the null hypothesis $H_0: P = P_0$ in favor of the alternative hypothesis $H_1: P = P_1$ with power $1 - \beta = 0.80$ (1-sided significance level $\alpha = 0.05$), 62 (eligible) patients are required in maintenance treatment arm with observation until progression (and at least 44 patients progression free at 12 months after randomization).

Taken into account that two parallel maintenance treatment arms will be analyzed (randomized 1:2 ibrutinib vs observation), we need 93 patient in both maintenance arms together. Given that the percentage of patients expected not to achieve MRD-neg after induction is 55% 207 patients are needed, and to overcome dropout due to ineligibility, 230 patients will be registered in the trial.

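### The 60% null is justified by a 1-year PFS under FCR, but the primary endpoint counts rescued progressions as successes, so passing 44/62 is not evidence of improvement on that figure

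*Protocol*

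**What the plan says.** Section 14.1 uses an A'Hern single-stage design for arm B alone: P0 = 60%, P1 = 75%, one-sided alpha 0.05, power 0.80, 62 eligible patients, and success if at least 44 are progression free 12 months after randomization. The only reason given for 60% is a published result in another population: "this assumption is based on a 1-year PFS of 60% for RR CLL patients treated with FCR for the PFS endpoint".

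Section 13.1 then defines success for this trial. The first allowance is "In this trial, reinitiated treatment due to MRD positivity will not be considered as progression". The same sentence adds a second: symptomatic CLL within 12 months is not progression either, if restarted treatment brings at least SD by 12 months after randomization. Section 14.4.1 repeats the second allowance with a different window: "If patients in the observation arm have clinical progression but achieve response within three months of reinitiating treatment, they are still considered progression free". It tests H0: rate at most 60% on this endpoint. Appendix B defines SD as neither PR nor PD.

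PFS by IWCLL criteria is listed separately as a secondary endpoint (synopsis; section 13.2). Section 14.4.6 makes every analysis except the primary one hypothesis-generating. Section 7 states that "no formal comparisons between the two randomized treatment arms will be made".

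**The concern.** The benchmark and the endpoint do not measure the same thing. The protocol presents the FCR figure as ordinary 1-year PFS, where a progression is a failure whatever happens next. In arm B, a patient who progresses off treatment, restarts both drugs and then merely stops progressing is a success. Nothing in section 14.1 adjusts the 60% for this.

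The 60% is described as the rate below which arm B does not merit a phase III trial, and the synopsis states the aim as long-lasting remission after stopping. A reader who sees the null rejected, with FCR as its stated source, will conclude that 12-month PFS after stopping beats the FCR result with 5% error. The test does not support that conclusion.

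Two further differences affect the same comparison. Arm B is selected: MRD negative in blood after cycle 12 and in blood and marrow at day 15 of cycle 15, with at least SD (section 8.2). Its 12 months run from randomization, after 15 cycles of treatment.

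**Working it through.** **Inputs.** From section 14.1: n = 62, cut-off 44, P0 = 0.60, P1 = 0.75. Not in the documents, therefore assumed: f, the share of conventional PFS failures in arm B that the rescue rule turns into successes.

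**Step 1: reproduce the plan's figures.** With X ~ Binomial(62, p):
- P(X ≥ 44 | p = 0.60) = 0.0492
- P(X ≥ 44 | p = 0.75) = 0.8121

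An exact search finds 62/44 to be the smallest design with alpha at most 0.05 and power at least 0.80. The design arithmetic is correct.

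**Step 2: link the two endpoints.** If conventional 12-month PFS is c, the modified success rate is c + (1 − c)f. At c = 0.60 this is 0.60 + 0.40f.

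**Step 3: chance of passing when conventional PFS is exactly 60%.**

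| Assumed f | Modified rate | P(X ≥ 44) |
|---|---|---|
| 0 | 0.60 | 4.9% |
| 0.05 | 0.62 | 9.1% |
| 0.10 | 0.64 | 15.6% |
| 0.25 | 0.70 | 49.6% |
| 0.375 | 0.75 | 81.2% |

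In the last row the modified rate equals P1, so the chance of passing equals the power.

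**Step 4: allow for deaths.** Death is a failure and cannot be rescued. If a fifth of failures are deaths (assumed) and 25% of the remainder are rescued, the modified rate is 0.60 + 0.40 × 0.80 × 0.25 = 0.68, and the chance of passing is 36.3% rather than 49.6%.

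**Step 5: what the 4.92% does protect against.** A modified rate of 60% corresponds to conventional PFS of (0.60 − f)/(1 − f). For f = 0.10 that is 0.50/0.90 = 55.6%; for f = 0.25 it is 0.35/0.75 = 46.7%. The 4.92% level applies to those conventional values, not to 60%.

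**Step 6: the rescue windows.** Sections 13.1 and 14.4.1 classify some patients differently, so f is not uniquely defined:
- Progression and restart at month 11 after randomization, first response at month 13: a success under 14.4.1 (within three months of restart), but not under 13.1 (after month 12).
- Progression and restart at month 2, SD first reached at month 6: a success under 13.1, but not under 14.4.1 (four months after restart).

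Section 7 has a third wording: three cycles of restarted therapy, or until 12 months after randomization if progression came within 9 months.

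**The case against.** The strongest reply is that alpha is stated for the protocol's own hypothesis. Section 14.1 calls P0 a success rate, section 14.4.1 tests the trial's own endpoint against 60%, and no passage claims superiority to FCR at 5% error. This stands. A reader might infer that the test's type I error is broken; it is not, because the level is 4.92% and the power 81.2% for the stated null. What is missing is a reason for 60% that applies to the endpoint being tested.

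The size of the effect depends on f, which is unknown, and late progressions leave little time for rescue under 13.1. This also stands, so no single error rate can be quoted. Only the direction is fixed: any rescue raises the success rate. Large values of f give near-certain success, but the documents do not establish that f is large.

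The FCR source was not available. That its figure contains no rescue allowance is inferred from the protocol calling it 1-year PFS and introducing the rescue rule as particular to this trial.

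A reader might also infer that the go/no-go decision should move to conventional PFS. The documents do not compel that. Stop-and-restart is a legitimate strategy to test, P1 = 75% was set for the present endpoint, and the move would leave the differences in population and time origin untouched. Nor is restart for MRD alone the core of the mismatch: without IWCLL progression it would not be a failure under conventional PFS either.

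Finally, IWCLL PFS and the number restarting are already secondary endpoints, and arm A is reported with its own curve. So the information will exist; what the protocol lacks is a rule tying the FCR comparison to it.

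**Conclusion.** The concern holds as a mismatch between the justification of P0 and the endpoint tested. Passing 44/62 shows, at 4.92% error, that more than 60% of arm B succeed under the stop-and-restart definition. It does not show improvement on the FCR 1-year PFS at that error: at conventional PFS of exactly 60%, the chance of passing is 9.1%, 15.6% or 49.6% for assumed rescued shares of 5%, 10% or 25%, and 36.3% at 25% if a fifth of failures are unrescuable deaths. This rests on an assumed f and on reading the FCR figure as ordinary PFS, as the protocol presents it. The sample size and cut-off are right for the stated null. The severity is below must-fix: the endpoint is openly defined, and the data for a like-for-like definition are to be collected.

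**What to change.** 1. In sections 14.1 and 14.4.1, keep the primary endpoint, n = 62 and the cut-off of 44, but label the endpoint success of the stop-and-restart strategy. Remove FCR as the justification for its 60%; state 60% as a clinical threshold, or justify it from data on the same definition.
2. Prespecify conventional 12-month IWCLL PFS in arm B, with progression or death a failure whatever follows and restart for MRD alone not a failure. Give an exact confidence interval beside the primary result. Section 14.4.1 builds the rescue allowance into its only definition of PFS, so say explicitly that this estimate is scored without it.
3. Let any statement relative to the FCR 60% rest on that estimate, noting that arm B is a selected MRD-negative group timed from randomization.
4. Reconcile the rescue windows in sections 7, 13.1 and 14.4.1, so that each patient has one classification.

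The cost is amended wording and one extra estimate, with no new patients or visits. The conventional figure cannot be more favourable than the primary one, and P1 = 75% and the 80% power were not set for it: at a true conventional PFS of 70%, for example, 44/62 would be reached only 49.6% of the time. That is a reason to report an interval rather than a second test.

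A descriptive B minus A difference in conventional PFS is optional. With 62 and 31 patients and assumed rates of 75% and 85%, its 95% half-width is 1.96 × √(0.75 × 0.25/62 + 0.85 × 0.15/31) = 0.166, about 17 points.

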8.2 Eligibility for randomization

- ◆ MRD negative peripheral blood after cycle 12.

- ◆ MRD negative peripheral blood and bone marrow at day 15 of cycle 15.
- ◆ At least SD after cycle 15.

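### The 60% null is taken from FCR-treated relapsed CLL patients but tested in an MRD-negative group counted from about month 14, so the 5% error rate does not apply to the state of being no better than FCR

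*Protocol*

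**What the plan says.** Section 14.1 uses an A'Hern one-stage design for arm B. P0 "has been taken as 60" percent and P1 "has been taken as 75" percent, with one-sided alpha 0.05 and power 0.80. This gives 62 eligible patients, of whom at least 44 must be progression free 12 months after randomization. A rate below 60% is regarded as not worth taking to phase III, and the support for that figure is that "this assumption is based on a 1-year PFS of 60% for RR CLL patients treated with FCR for the PFS endpoint".

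The group tested is narrower. Section 8.2 requires MRD-negative blood after cycle 12, MRD-negative blood and marrow at day 15 of cycle 15, and "At least SD after cycle 15". Section 14.1 expects 45% of registered patients to reach randomization. Section 14.4.1 states the hypothesis as a rate 12 months after randomization. On MRD and prognosis, section 14.1 says: "Patients who are MRD positive continuing on maintenance ibrutinib are expected to have a lower PFS than MRD negative patients".

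**The concern.** The null rate and the group it is tested in differ in two ways: who is counted, and from when. The FCR figure is described simply as a 1-year PFS in treated relapsed or refractory patients. Arm B is selected on deep response and on not having progressed during 15 cycles. By the protocol's own expectation about MRD, a rate from patients not selected on MRD should understate the rate in an MRD-negative subset.

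What is at stake is the meaning of a positive result. Section 14.4.6 treats the primary analysis as the confirmatory one and does not let later deviations touch it. If 44 of 62 is reached, the FCR clause invites the conclusion that stopping treatment does better than FCR with 5% error. That error rate was calculated for a different statement.

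**Working it through.** **Inputs.** From 14.1: n = 62, cut-off 44, P0 = 0.60, P1 = 0.75, one-sided alpha 0.05, power 0.80, 93 randomized 1:2. From 9.1: 28-day cycles. From 15.3: randomization within 14 days of the MRD test at day 15 of cycle 15.

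**1. The plan's own figures.** With X binomial(62, p):
- P(X ≥ 44 | p = 0.60) = 0.049
- P(X ≥ 44 | p = 0.75) = 0.812

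A search for the smallest n with exact alpha ≤ 0.05 and power ≥ 0.80 also returns n = 62 with cut-off 44. The design reproduces.

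**2. When the clock starts.** 15 × 28 = 420 days, and 420 / 30.4375 = 13.8 months. Day 15 of cycle 15 is day 14 × 28 + 15 = 407, or 13.4 months. Arm B is therefore counted from about month 14 after treatment start.

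**3. What the rule does if the comparable FCR rate is not 60%.** Let q be the 12-month PFS that FCR would show in patients selected and counted as in arm B. The documents do not give q, so it is varied as an assumption:

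| Assumed q | P(X ≥ 44 of 62) |
|---|---|
| 60% | 0.049 |
| 65% | 0.198 |
| 70% | 0.496 |
| 75% | 0.812 |
| 80% | 0.969 |

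The even-odds point is q of about 70%. For scale, suppose the hazard is constant and MRD-negative patients have 0.7 times the hazard of the whole FCR group (an assumption). Then q = 0.60^0.7 = 0.699 and the rule passes with probability 0.49.

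**4. The later clock on its own.** Take a Weibull curve with S(12 months) = 0.60 and cumulative hazard H(t) = −ln(0.60) × (t/12)^k. The conditional 12-month PFS is exp{−[H(25.8) − H(13.8)]}:

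| Shape k | Conditional PFS | P(X ≥ 44 of 62) |
|---|---|---|
| 0.7 (falling hazard) | 73.4% | 0.72 |
| 1.0 (constant) | 60.0% | 0.049 |
| 1.2 (rising) | 50.9% | 0.001 |

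The late start can raise, leave or lower the rate. The upward direction that the protocol itself supports comes from MRD selection.

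**5. Precision of an arm B minus arm A difference.** Arm A has 93 − 62 = 31 patients. Assuming 75% in B and 80% in A: 1.96 × √(0.75 × 0.25/62 + 0.80 × 0.20/31) = 1.96 × 0.0905 = 0.177, about ±18 percentage points.

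**The case against.** The strongest reply is that the protocol never claims a gain over FCR. The tested hypothesis in 14.4.1 is only whether arm B exceeds 60%, the 60% works as a go/no-go floor, and both error rates are right for that hypothesis. This stands as far as it goes: neither the test nor the sample size is wrong. It does not remove the point, because the only support 14.1 offers for the floor is the FCR figure.

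A second reply is that case mix may pull the other way. Entry allows any number of prior lines, performance status 3 if due to CLL, and TP53 aberrations. This also stands: the documents do not show whether arm B's prognosis exceeds that of the FCR cohort. That cohort is itself described in one clause. The title in the reference list concerns salvage after first relapse following FCR, so the sponsor should confirm which patients the 60% describes and from what time origin.

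A reader might go further and infer that the rule passes most of the time with no gain over FCR. One route is to split a 60% average into 45% MRD-negative and 55% MRD-positive patients and solve for the MRD-negative rate. The documents do not support that sum. It puts a rate counted from randomization into an average for a rate naturally read as starting with treatment, and patients who failed before month 14 carry weight although they have no post-randomization rate. It also borrows the 45%, which is this regimen's expected share, for a regimen assumed no better than FCR. Another route is a model in which frail patients fail early. Such a model makes the hazard fall by construction, so it can only raise the rate. With a constant or rising hazard the late clock gives no increase.

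**Conclusion.** The point holds in a limited form. The 60% null is justified by a group that differs from arm B in selection and time origin, and the protocol's own statement on MRD says the selection favours a higher rate. The exact error of 0.049 is correct for a true arm B rate of 60%. It is not the error for a strategy no better than FCR.

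The size cannot be fixed from the documents. It runs from 5% to 97% as the assumed comparable rate goes from 60% to 80%, and passing becomes more likely than not only above about 70%, a figure no document states. The conclusion rests on reading the FCR figure as unselected by MRD and counted from treatment start, which is the natural reading of 14.1 but is not spelled out. The change should be made because it alters what may be concluded from a positive result, not because the design calculation fails.

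**What to change.** **Section 14.1.** Keep 62 patients and the cut-off of 44. State that 60% is a fixed minimum-activity threshold for the MRD-negative population that stops treatment. Remove the FCR clause as its justification, and state that crossing the threshold does not show a gain over FCR. A higher cut-off is not proposed, because the documents hold no comparable FCR rate from which to set one.

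**Section 14.4.1.** Beside the arm B result, report descriptively the 12-month PFS from randomization in arm A and the B minus A difference with a 95% confidence interval. Arm A is the only group selected in the same way and counted from the same time. Use the standard IWCLL definition of PFS in both arms for this estimate. The primary endpoint's retreatment exemption (section 13.1) concerns arm B only and would make the difference uneven. Label it descriptive, in line with the protocol's statement that the randomized arms are not formally compared.

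The planned all-patient curve from registration should not be offered as evidence on stopping: 12 months from registration falls before the 420 days of scheduled induction are over.

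**Cost.** Wording in two sections and extra estimates from data already collected, with no extra patients. The claim becomes more modest, and the difference will be imprecise, about ±18 points under the assumed 75% and 80%.
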